### 4.4 Sample size calculations

The primary research question is does treatment with metformin result in a gain in the median length of gestation of greater than or equal to 5 days compared to the mother receiving placebo therapy. This magnitude of prolongation we believe to be a clinically important difference and likely to have important beneficial implications for the fetus (although perinatal outcomes will not be a primary outcome in this phase II study).

Given the focus on median prolongation and the skewed nature of the gestation prolongation (seen in the two trials listed below) we based sample size calculations on the Geometric Mean Ratio (GMR). Analysis was performed both using PASS 13 (Power Analysis and Sample Size Software (2014). NCSS, LLC. Kaysville, Utah, USA, [ncss.com/software/pass](http://ncss.com/software/pass)) and the Powercal program running in Stata v15 (Stata statistical software. 2017 Release 15. Stata Corp. College Station, TX: StataCorp LLC).

Power calculations settings were: 90% power, with two-sided alpha set at 0.05, control median prolongation of 8.3 days and clinically important prolongation of gestation of 5 days. The measure of variability used in this analysis is the Coefficient of Variation (CV) = (data SD)/ data Mean) in mothers treated with standard expectant management. We have two sources for gestational prolongation in pre-eclamptic mothers receiving expectant management after PE diagnosis both undertaken at the same hospital where we plan to run this trial (Tygerberg Hospital). The first was by Hall et al, who in the largest descriptive study on expectant management of early onset pre-eclampsia reported a mean gestation prolongation of 11 (SD 7) days equivalent to a CV = 0.64. The second was the PIE trial, performed by [name] et al, where patients randomized to the placebo arm had an overall mean prolongation of 13.1 (SD 12.2) days, a CV = 0.93. In this study mothers entering with greater than 29 week gestations the CV = 0.8. We have chosen to use a CV = 1.0, slightly larger than the 0.93 found in our PIE study, to allow for adequate power if greater variability in prolongation times occurs in PI2.

The results of sample size requirements for a limited range of GMR and two CVs are presented in table 1.

Table 1: Sample size calculation

Detectable prolongation in median days*	Treated group Median	GMR	Number per group (CV = 1.0)	Number per group (CV = 0.93)	Number per group (CV = 0.80)
3.11	11.43	1.37	137	134	105
4	12.32	1.48	88	87	69
5	13.32	1.6	65	61	49

\*placebo group median = 8.32 days

Using a CV = 1.0, 65 patients are required per group. Allowing for 10 dropouts/group, we require 75 patients per arm..

The gestational age at diagnosis is likely to affect allowable length of pregnancy prolongation. For instance, those diagnosed at 31+6 will be delivered at 34 weeks (should they reach that gestation), as it is unit policy to deliver at that gestation. Thus, such patients will have a maximum length of pregnancy prolongation of 15 days. In contrast, those diagnosed at 28 could conceivably obtain many weeks of pregnancy prolongation (if the disease remains stabilised). Further it is possible that metformin efficacy may vary with gestational age at diagnosis.

To ensure treatment group allocation is balanced for this potential variable, we will stratify randomisation into strata based on gestational age.

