management (control group). Two studies were used provided estimates for the expected gestational prolongation and associated CV in pre-eclamptic mothers receiving expectant management after PE diagnosis (control group) on two studies ². The first by Hall et al reported a mean gestation prolongation of 11 (SD 7) days equivalent to a CV = 0.64, whilst the second by [name] et al (PIE 1 study) reported an overall mean prolongation of 13.1 (SD 12.2) days in the placebo arm, a CV = 0.93. In the PIE 1 study mothers entering at a gestation greater than 29 weeks had a CV = 0.8. We have chosen to use a CV = 1.0, slightly larger than the 0.93 found in the overall PIE study, to maintain adequate power if slightly greater variability in prolongation times occurs. The results of sample size estimates for a limited range of GMR and two CVs are presented in the following table:

Detectable prolongation in median days*	Treated group Median	GMR	Number per group (CV = 1.0)	Number per group (CV = 0.93)	Number per group (CV = 0.80)
3.11	11.43	1.37	137	134	105
4	12.32	1.48	88	87	69
5	13.32	1.6	65	61	49

*placebo group median = 8.32 days

Therefore, at analysis we require 65 patients per trial arm. Allowing for 10 dropouts within each arm we plan to recruit 150 patients (75 patients in the placebo & 75 in the treatment arms). The dropouts, including patient requested trial withdrawal and delivery before any trial medication was given occurred in 6/119 (5.0%) of mothers.

Whilst presentation of results will include Kaplan-Meier survivorship curves and adjusted hazard ratios for a Cox proportional hazards model the following power analysis based upon expected events indicates that this study is not adequately powered to use survivorship as the primary endpoint. In the setting of this trial the Hazard Ratio (HR) defined as the time for control/time for Rx at the same proportion of survival. For example, taking the median survival time of 9 days in the control group from the Hall study we can assess the HR detected for the predetermined group size:

Time above median (days)	Median time in Rx group (days)	HR	Group size (equal group size)
3	12	0.75	360
4	13	0.69	225
5	14	0.64	158
6	15	0.60	120
7	16	0.56	96
8	17	0.53	80
9	18	0.50	68
13.5	22.5	0.40	42

² [name] CA, Hannan NJ, van Papendorp E, et al. Esomeprazole to treat women with preterm preeclampsia: a randomized placebo-controlled trial. Am J Obstet Gynecol 2018;219:388.e1-17

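### The 90% power rests on an unchecked conversion from a raw-scale CV to a log-scale SD, and the plan's likely source arm does not fit that conversion

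*Protocol*

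**What the plan says.** Protocol 4.4 sets "90% power, with two-sided alpha set at 0.05, control median prolongation of 8.3 days and clinically important prolongation of gestation of 5 days". Table 1 turns this into a treated median of 13.32 days against 8.32, a ratio of 1.6. The variability input is defined on the raw scale: "The measure of variability used in this analysis is the Coefficient of Variation (CV) = (data SD)/ data Mean".

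Two sources are given for it. The descriptive study of expectant management at the same hospital has mean 11 (SD 7), CV 0.64. For the esomeprazole trial, "patients randomized to the placebo arm had an overall mean prolongation of 13.1 (SD 12.2) days, a CV = 0.93". The plan then goes above both: "We have chosen to use a CV = 1.0, slightly larger than the 0.93 found in our PIE study, to allow for adequate power". SAP 11 repeats this choice.

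The control median appears only as 8.3 in the text and, under Table 1, as "placebo group median = 8.32 days", with no source. SAP 11 gives the descriptive study's median as 9 days. The result is 65 per arm, raised to 75 for dropouts. Protocol 14.2 then describes the study, without qualification, as powered for a five-day gain.

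**The concern.** A test of a geometric mean ratio depends on the spread of log prolongation. Neither document reports that spread, and neither states that prolongation is taken to be lognormal. A raw CV fixes the log-SD only if the shape is known, and a lognormal ties the mean/median ratio to the CV. The printed control mean and median can therefore be used to check the conversion.

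At stake is how a null result is read. With 90% power, a null result would count as fairly strong evidence against a five-day gain; with 80% it counts for noticeably less. CV 1.0 is also offered as protection against greater variability, which discourages anyone from rechecking it. Replacing the power formula with one for another test would not help if the same converted input were carried over.

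**Working it through.** **Inputs.** Two-sided alpha 0.05, power 90%, control median 8.32, treated median 13.32, CV 1.0, 65 and 75 per arm (Protocol 4.4, Table 1); control means 13.1 (SD 12.2) and 11 (SD 7) (Protocol 4.4); descriptive-study median 9 (SAP 11). Powers are for a two-sample t-test on log days (noncentral t).

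**1. Reproduce the plan.** The effect is ln(1.6) = 0.470. The lognormal conversion is log-SD = sqrt(ln(1 + CV²)), which gives 0.833 at CV 1.0, 0.789 at 0.93 and 0.703 at 0.80. Numbers per arm for 90% power:

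| Ratio | CV 1.0 printed / computed | CV 0.93 printed / computed | CV 0.80 printed / computed |
|---|---|---|---|
| 1.37 | 137 / 146–148 | 134 / 131–134 | 105 / 105–106 |
| 1.48 | 88 / 96 | 87 / 86–87 | 69 / 69 |
| 1.60 | 65 / 67 | 61 / 61 | 49 / 48–49 |

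Ranges reflect using the rounded ratio or the printed medians. Using CV 1.0 directly as the log-SD would need 96 per arm at ratio 1.6, far from 65, so the lognormal conversion was used. The other two entries in the CV 1.0 column do not reproduce. Power at CV 1.0 is 89% at 65 per arm and 93% at 75.

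**2. Check the shape.** For a lognormal, mean/median = sqrt(1 + CV²).
- A mean of 13.1 implies a median of 13.1/1.366 = 9.59 at CV 0.93 and 13.1/1.414 = 9.26 at CV 1.0. The plan uses 8.32.
- Conversely, 13.1/8.32 = 1.575, so log-SD = sqrt(2 ln 1.575) = 0.953 and CV = sqrt(1.575² − 1) = 1.22.

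**3. Effect on the plan's own formula.** With log-SD 0.953, power for ratio 1.6 is 80% at 65 per arm and 85% at 75. Reaching 90% needs 88 per arm. The gain detectable with 90% power is about 6.0 days at 65 and 5.5 days at 75.

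**4. Other pairings of the printed control figures** (ratio held at 1.6):

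| Mean / median | Log-SD | Power, 65 per arm | Power, 75 per arm |
|---|---|---|---|
| 13.1 / 8.32 | 0.953 | 79.7% | 85.1% |
| 13.1 / 9 | 0.866 | 86.6% | 91.0% |
| 11 / 8.32 | 0.747 | 94.5% | 96.9% |
| 11 / 9 | 0.633 | 98.7% | 99.5% |

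Using CV 0.93 as the plan does gives 92% at 65 per arm. SD 12.2 with median 8.32 gives log-SD 0.847 and 88%. Mean 13.1 with SD 12.2 taken as lognormal puts the median at 9.6, so five days is ratio 14.6/9.6 = 1.52, and power is 85%.

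**5. Could the mismatch be chance?** The size of the placebo arm is not given; assume 60. In simulated samples of 60 from a lognormal, mean/median reaches 1.57 in about 15% of samples at CV 1.0 and about 8% at CV 0.93.

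**6. Planned test.** SAP 23 and 24 specify median regression on untransformed days. A rough simulation (lognormal times, a stratum term, 65 per arm) gives power near 0.7 at log-SD 0.83 and near 0.6 at 0.95. The log-scale figures above are therefore not the power of the primary analysis.

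**The case against.** The strongest reply is that nothing has been shown to be wrong. Neither document says that 8.32 and 13.1 describe the same women. Even if they do, a ratio of 1.57 is within ordinary sampling variation for an arm of about 60. CV 1.0 is indeed larger than the 0.93 that was observed. The trial recruits 75 per arm, SAP 11 cites 5.0% dropouts in earlier experience, and SAP 25 expects no missing primary outcome, so 65 is a pessimistic analysed number. All of this stands, and it limits the conclusion.

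It does not rescue the 90%. The 8.32 is labelled a placebo median; only one cited source has a placebo arm, and the other source's median is given as 9. If the shared-arm inference is wrong, a key input has no documented source. The plan itself set aside the descriptive study's smaller CV, so the high powers from that study's mean are weak support.

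Two stronger readings are tempting. A reader might infer that power falls below 90% however the control figures are read. It does not: several readings in the working exceed 90% at 65 per arm. A reader might also infer from SAP 11's hazard-ratio definition ("In the setting of this trial the Hazard Ratio (HR) defined as the time for control/time for Rx at the same proportion of survival") that times are taken as exponential, which has CV 1.0 but a much larger log-SD, so that one CV carries two meanings. No CV enters that table. It starts from the descriptive study's 9-day median and serves only to explain why survival is not the primary endpoint.

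**Conclusion.** The point holds in a limited form. The stated 90% depends on a lognormal conversion that is neither declared nor checked, and the arm that most likely supplied the control figures does not fit it. If 13.1 and 8.32 share that arm and times are lognormal, log-scale power for five days is about 80% at 65 per arm and 85% at 75. Across the mean and median pairings the range at 65 per arm is about 80% to 99%. The 90% is unsupported rather than disproved, and CV 1.0 is not shown to be conservative. Confidence is medium, because the source of 8.32, the size of the placebo arm and the true log-SD are not in the documents. The point should be corrected before results are interpreted, but it does not call for a change in sample size or primary analysis.

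**What to change.** Keep 150 women, and:

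- State the source of the 8.32-day median in Protocol 4.4 and SAP 11.
- Replace the converted CV with the observed distribution of prolongation times in the esomeprazole trial's placebo arm, which is the team's own completed trial at the same hospital.
- Resample those times to obtain power for the planned stratum-adjusted median regression on untransformed days, at 65 and 75 per arm. Apply the zero-prolongation rule for fetal demise (SAP 23) and the 34-week delivery ceiling (Protocol 4.4, SAP 11). Working on untransformed days also avoids taking the log of zero.
- Recheck the CV 1.0 column of the sample size table in both documents.
- Restate power and detectable gain in Protocol 4.4, Protocol 14.2 and SAP 11.

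If only the printed figures can be used, give the log-scale range with its assumptions, say that it is not the power of the median regression, and remove the statement that CV 1.0 provides a margin.

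The cost is a short re-analysis of in-house data and wording changes in three places, with no extra patients. The downside is that the stated power will probably be less favourable.

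### Two entries in the CV = 1.0 column of the sample-size table (137 and 88 per group) are about 6–8% too low; the design entry of 65 is 1–2 women short and the planned 75 per arm is unaffected

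*Protocol*

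**What the plan says.** Protocol 4.4 gives the settings: "Power calculations settings were: 90% power, with two-sided alpha set at 0.05", a GMR-based calculation, a "clinically important prolongation of gestation of 5 days", and, under Table 1, "placebo group median = 8.32 days". Variability enters as a coefficient of variation (CV). The protocol chooses CV = 1.0, above the 0.93 seen in the placebo arm of the earlier esomeprazole trial at the same hospital, as protection against greater variability. Allocation is 1:1 (protocol 4.5, SAP section 10).

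Table 1 lists the number per group for three differences in median:

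| Difference (days) | GMR | CV 1.0 | CV 0.93 | CV 0.80 |
|---|---|---|---|---|
| 3.11 | 1.37 | 137 | 134 | 105 |
| 4 | 1.48 | 88 | 87 | 69 |
| 5 | 1.6 | 65 | 61 | 49 |

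From the last row the protocol concludes "Using a CV = 1.0, 65 patients are required per group". SAP section 11 carries the same table and says "Therefore, at analysis we require 65 patients per trial arm". Both documents add 10 per arm for dropout, giving 75 per arm and 150 in total.

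**The concern.** The CV = 1.0 column barely differs from the CV = 0.93 column in the two upper rows (137 against 134, 88 against 87). With the GMR, alpha and power fixed, the required number is proportional to the log-scale variance, so this change in CV should raise every row by the same proportion, about 11%. The table rises by 2%, 1% and 7%.

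CV = 1.0 is the value that the protocol adopts as its safety margin, so this is the column where the price of that margin should be right. As printed, allowing for CV 1.0 appears to cost 3 and 1 extra women per group in the upper rows, when it costs about 14 and 9. Protocol 14.2 says that the trial is underpowered for shorter prolongations that would still be of benefit, and it foresees a larger trial if metformin works. A reader planning for a 3- or 4-day effect would look to these two rows.

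**Working it through.** **Inputs.** Two-sided alpha 0.05, power 90%, CVs of 1.0, 0.93 and 0.80, and medians of 8.32 (placebo) and 11.43, 12.32 and 13.32 (treated), all from protocol 4.4; 1:1 allocation from protocol 4.5. The documents name two programs but not the test or the rounding rule, so the log-normal two-sample comparison is an assumption. Step 1 tests it against the table.

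**Formula.** Effect d = ln(GMR). Log-scale variance s² = ln(1 + CV²). Normal approximation: n per group = 2 × s² × (1.960 + 1.282)² / d², where (1.960 + 1.282)² = 10.51. The exact version uses the non-central t with 2n − 2 degrees of freedom and adds one or two patients per group.

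**Step 1: reproduce the plan's other two columns.** s² = ln(1.8649) = 0.6232 at CV 0.93 and ln(1.64) = 0.4947 at CV 0.80. With the GMRs as printed, exact t:

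| GMR | CV 0.93: stated / computed | CV 0.80: stated / computed |
|---|---|---|
| 1.37 | 134 / 134 | 105 / 106 |
| 1.48 | 87 / 87 | 69 / 69 |
| 1.6 | 61 / 61 | 49 / 49 |

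All six cells agree within one patient, which identifies the method.

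**Step 2: apply it at CV 1.0.** s² = ln 2 = 0.6931, so SD = 0.8326.

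- GMR 1.37: d = 0.3148; n = 2 × 0.6931 × 10.51 / 0.0991 ≈ 147 (normal), 148 (exact t). With the unrounded ratio 11.43/8.32 = 1.3738: 145 and 146.
- GMR 1.48: d = 0.3920; n = 94.8, so 95 (normal), 96 (exact t). The unrounded ratio gives the same.
- GMR 1.6: d = 0.4700; n = 65.94, so 66 (normal), 67 (exact t). The unrounded ratio gives the same.

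| GMR | Stated | Required (exact t) | Shortfall | Power at stated n: exact t / normal |
|---|---|---|---|---|
| 1.37 | 137 | 148 (146 unrounded) | 11 (9) | 0.877 / 0.879 (0.882 / 0.884) |
| 1.48 | 88 | 96 | 8 | 0.874 / 0.878 |
| 1.6 | 65 | 67 | 2 | 0.891 / 0.896 |

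As a proportion, 137 is 6.2% below 146 and 7.4% below 148; 88 is 7.4% below 95 and 8.3% below 96.

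**Step 3: check the columns against each other.** From CV 0.93 to 1.0 the ratio of required numbers is 0.6931 / 0.6232 = 1.112 in every row. The table gives 137/134 = 1.022, 88/87 = 1.011 and 65/61 = 1.066. Solving the normal formula backwards, the three stated entries correspond to CVs of 0.953, 0.950 and 0.990, so no single CV produces the column.

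**Step 4: consequence for the trial.** At CV 1.0 and GMR 1.6, exact-t power is 0.930 with 75 per arm. SAP section 11 quotes dropout of 6/119 (5.0%); 75 × 113/119 = 71.2, and 71 per arm gives 0.916.

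**The case against.** The strongest reply is that the one cell the trial uses is right for practical purposes. On the normal approximation 65.94 women are needed per group, or 65.5 with the 13.3/8.3 medians implied by the rounded figure in the text, so rounding down instead of up explains 65, and power is then 0.896–0.898. Since the test and rounding rule are not stated, insisting on 67 is partly a choice of convention. The planning CV is also a deliberate cushion: at 0.93 the requirement is 61, which 65 exceeds. The 3.11- and 4-day rows set no sample size, analysis or decision rule, and the trial, at 65–75 per arm, is too small for those effects on either the printed or the corrected figures.

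Most of this stands, and it is why the point is minor. It does not rescue 137 and 88, which miss under both the normal and the exact calculation, with rounded and unrounded ratios alike. Nor does it explain why the column rises by different proportions from its neighbour. On convention, 61 and 49 in the design row match the exact t, so 67 is the consistent companion figure.

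A reader might infer that the trial's sample size was miscalculated, or that the trial is underpowered for its 5-day target. The documents do not support that: the design cell is within 1–2 women of the requirement, and the recruitment target leaves room above it.

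**Conclusion.** The CV = 1.0 entries for 3.11 and 4 days are wrong as written in both documents: about 146–148 and 95–96 per group are needed, against 137 and 88, and the printed sizes carry about 87–88% power. The design entry of 65 gives about 89% power and is 1–2 women short, a gap close to rounding. The planned 75 per arm meets the 90% target, with about 93% power if all are analysed and about 92% at the quoted dropout. Severity is minor.

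This rests on the log-normal two-sample model, which the documents do not spell out but which the other six cells confirm. It says nothing about the power of the median quantile regression specified as the primary analysis (protocol 8.6, SAP section 24).

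**What to change.** In protocol Table 1 and the matching table in SAP section 11, restate the CV = 1.0 column as 148, 96 and 67 (146 in the first row if unrounded medians are used; state which). In the sentence under each table, either keep 65 and say that it gives about 89% power, or give 67 as the requirement. State the test and rounding rule used. Add one line saying that 75 per arm meets the 90% target on this planning model, at about 93% with all analysed and about 92% after 5% dropout.

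The cost is three cells and a sentence or two in each document. Recruitment does not change. If 67 is adopted, the stated dropout margin falls from 10 to 8 per arm (75 − 67), which is 10.7% and still about twice the quoted dropout rate; the later statements in SAP section 11 that use 65 per arm would then need to be brought into line.

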**Table 2: Gestational age stratification**

	Gestational age (GA)	EFW if GA is unknown
Strata 1	26 +0 up to and including 28+6 weeks	Less than and including 1100 grams
Strata 2	29+0 up to and including 31+6	Greater than 1100 grams

Stratified randomisation will ensure that the number of participants in each gestational age stratum is balanced.

## **4.5 Randomisation and allocation concealment**

Randomisation will be done in an equal ratio of metformin to placebo. An online, web-based sequence generator system will be used to avoid chance imbalances in the stratification process. It will be linked with codes for placebo and treatment tablets provided by the manufacturer contracted to produce the trial medication. Researchers and participants will both be blinded.

Randomization will include blocking within each stratum. Blocking ensures that the control and treatment group numbers remain close both within the strata and overall. We propose using blocks of 4 to 6 with the size and order randomly assigned. Its use of stratified randomization ensures balance between treatment and control groups for gestational age however its use induces within stratum correlation. We will take this into account in the analysis by treating strata as covariates in regression analysis.

Once the participants have been randomised the treatment pack with the same code will be allocated to the participant. All treatment packs will be identical and will contain either active tablets or placebo. The treatment packs will be prepared by the manufacturer contracted to produce the trial medication. The researchers will have no access to the randomisation list. This

process will ensure that there is allocation concealment throughout the conduct of the trial. The allocation will only be released once the trial is completed.

## Inclusion and exclusion criteria

### 5.1 Definitions:

There are many classification systems for the hypertensive disorders of pregnancy. The International Society for the Study of Hypertensive Disorders in Pregnancy (ISSHP) published a new classification system for hypertensive disorders in pregnancy in 2014. We will use this classification system in this study.

The following definitions are used in this classification system:

**Hypertension in pregnancy:** office or in hospital systolic blood pressure greater than or equal to 140 mmHg and/or a diastolic blood pressure greater than or equal to 90 mmHg on the average of at least two measurements, taken at least 15 minutes apart, using the same arm.

**Severe Hypertension:** systolic blood pressure greater than or equal to 160 mmHg or a diastolic blood pressure greater than or equal to 110 mmHg on the average of at least two measurements, taken at least 15 minutes apart, using the same arm.

**Pre-existing (chronic) hypertension:** hypertension that pre-dates the pregnancy or appears before 20 weeks gestation.

**Gestational Hypertension:** hypertension that appears at or after 20 weeks of gestation.

**Pre-eclampsia:** gestational hypertension and new proteinuria or one or more adverse conditions or one or more serious complications (see table 3 for definitions of adverse conditions and serious complications).

**Adverse condition:** consists of maternal symptoms, signs, abnormal laboratory results and abnormal fetal monitoring that may herald the development of severe maternal or fetal complications.

**Significant proteinuria:** greater than or equal to 0,3 g/d in a complete 24-hour urine collection or a spot (random) urine sample with greater than or equal to 30 mg/mmol urinary creatinine.

**Severe pre-eclampsia:** pre-eclampsia associated with a severe complication that warrants delivery regardless of gestational age.

